### 11.5.2. Study Population

Age

 
GSK standard IDSL algorithms will be used for calculating age where birth date will be imputed as follows: 
 
Any participant with a missing day will have this imputed as day '15'.
 
Any participant with a missing day and month will have this imputed as '30th June'.
 
 
 
Birth date will be presented in listings as 'YYYY'.
 
Completely missing dates of birth will remain as missing, with no imputation applied. Consequently, the age of the subject will not be calculated and will remain missing.
 

Body Mass Index (BMI)

 
Calculated in the CRF as Weight (kg) / [Height (m)]
 

[figure not shown]
### 11.5.3. Safety

Exposure	
Compliance	
Compliance for the OLI Phase will be calculated as follows:	
$\text{OLI Compliance \%} = \frac{\text{# days subject took the study drug}}{\text{Minimum (# of days subject was enrolled in the OLI period, 28)}}$	
Extent of Exposure	

 
Exposure to CAB+RPV Oral Lead-in = IP (oral lead-in) stop date - IP (oral lead-in) start date +1
 
	
Duration (Days)	

 
AE Resolution Date – AE Start Date + 1
 
	
Laboratory Parameters	

 
If a laboratory value which is expected to have a numeric value for summary purposes, has a non-detectable level reported in the database, where the numeric value is missing, but typically a character value starting with '<x' or '>x' (or indicated as less than x or greater than x in the comment field) is present, the number of significant digits in the observed values will be used to determine how much to add or subtract in order to impute the corresponding numeric value. If a character value starting with "<=x", then the numeric value will be x. 
 
Example 1: 2 Significant Digits = '< x ' becomes x – 0.01
 
Example 2: 1 Significant Digit = '> x' or '>=x' becomes x + 0.1
 
 
 
	
Example 3: 0 Significant Digits = '< x' becomes x – 1	
12-Lead Electrocardiograms	
QTcB Interval	
When not entered directly in the eCRF, corrected QT intervals by Bazett's (QTcB) and Fridericia's (QTcF) formulas will be calculated, in msec, depending on the availability of other measurements.	
If RR interval (in msec) is provided, then missing QTcB and/or QTcF will be derived as	
$\text{QTcB} = \frac{\text{QT}}{\sqrt{\text{RR}/1000}}$	$\text{QTcF} = \frac{\text{QT}}{\sqrt[3]{\text{RR}/1000}}$
where uncorrected QT interval is also measured in msec.	
If RR interval is not provided directly and one of QTcB or QTcF has been entered, then RR interval can be obtained from the above formulas and used to calculate the other correction method value; i.e.,	
$\text{QTcB} = \sqrt{\frac{\text{QTcF}^3}{\text{QT}}}$	$\text{QTcF} = \sqrt[3]{\text{QT} \cdot \text{QTcB}^2}$

#### 11.5.4. Pharmacokinetic

Pharmacokinetic Parameter Statistics

For the purposes of calculating summary statistics and for statistical analysis, all PK parameters with the exception of <math>t_{max}</math> will be <math>\log_e</math> transformed.

Geometric coefficient of variation:

Untransformed Data: <math>100 * (SD/Mean)</math>.

Transformed Data: <math>100 * (\sqrt{\exp(SD_{\log}^2)} - 1)</math> where <math>SD_{\log}</math> indicates the standard deviation of log-transformed data

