**Table 2      Model Predicted Exposure Parameters of CAB and RPV Following A Single IM Injection in *Gluteus Medius***

Parameter	Units	CAB	RPV
		Median (90% PI)	Median (90% PI)
KALA	/h	0.00064 (0.0002, 0.0018)	0.000146 (0.000145, 0.000164)
Half-Life	Weeks	6.5 (2.3, 20.9)	28.1 ( 25.1 - 28.4)
Tmax	days	8 (5, 15)	4.0 (3.0 - 31.0)
Cmax	µg/mL	2.13 (0.69, 5.80)	56.0 (21.2 - 151)
C wk4	µg/mL	1.56 (0.63, 2.96)	34.6 (17.5 - 69.3)
C wk8	µg/mL	0.91 (0.43, 1.57)	20.3 ( 10.4 - 38.3)
C wk12	µg/mL	0.58 (0.18, 1.03)	13.5 (6.75 - 25.6)

Parameter	Units	CAB	RPV
		Median (90% PI)	Median (90% PI)
C Wk24	µg/mL	0.18 (0.025, 0.45)	6.98 ( 3.33 - 13.6)
C Wk36	µg/mL	0.05 (0.025, 0.26)	4.88 ( 2.26 - 9.68)
C Wk48	µg/mL	0.025 (0.025, 0.16)	3.58 ( 1.66 - 7.15)
C Wk52	µg/mL	0.025 (0.025, 0.14)	3.24 ( 1.50 - 6.49)
AUC 0-Wk4	µg*h/mL	1216 (422, 2857)	28354 (10674 - 67476)
AUC 0-Wk8	µg*h/mL	2080 (811, 4132)	47419 (21949 - 99140)
AUC 0-Wk12	µg*h/mL	2601 (1133, 4763)	58909 (29731 - 116809)
AUC 0-Wk24	µg*h/mL	3271 (1788, 5461)	78560 (43502 - 144786)
AUC 0-Wk36	µg*h/mL	3519 (2082, 5738)	91349 (51528 - 164003)
AUC 0-Wk48	µg*h/mL	3634 (2215, 5852)	100079 (56879 - 178154)
AUC 0-Wk52	µg*h/mL	3655 (2240, 5868)	102380 (58332 - 182124)

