### 3.2. Final Analyses

Final analysis will be performed after all subjects have completed the study and final database freeze (DBF) has been declared by Data Management. Data will be listed and summarized according to GSK reporting standards, where applicable.

Statistical data analyses will be performed by, or under the direct auspices of, Clinical Statistics and Programming, GlaxoSmithKline utilizing SAS version 9.4 or higher. PK analysis of the plasma CAB and RPV concentration-time data will be conducted using non-compartmental methods with WinNonlin (Version 6.3 or higher).

All the derived PK parameters will be listed and summarized by treatment and study phase. For each of these PK parameters the following descriptive summary statistics will be calculated: n, arithmetic mean with associated 95% CI, standard deviation, median, minimum, and maximum. The mean & geometric mean with associated 95% CIs, standard deviations, and geometric coefficient of variation (CVb(%)) will also be calculated for all parameters except tmax.

Safety and health outcome data will be presented in tabular and/or graphical format and summarized descriptively according to GSK's Integrated Data Standards Library (IDSL) standards.

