### 8.1. Drug Concentration Measures

Plasma CAB and RPV concentration values will be summarized with descriptive statistics by study phase, treatment, visit, and planned timepoint for the PK Concentration Population (PC). These concentration values will be determined directly from concentration-time data from each analyte. Descriptive statistics including the n, mean with associated 95% CI, standard deviation, median, minimum, maximum, geometric mean with associated 95% CI, standard deviation of logarithmically transformed data, 5th/95th percentiles and the geometric coefficient of variation (CVb(%))).

Individual concentration-time profiles and median/mean profiles from each analyte in each study phase will be plotted for the PK Concentration (PC) Population. Each of the figures will contain one plot on the untransformed scale (i.e. a linear plot) and one plot on the log transformed scale (i.e. semi-log plot). Actual assessment times will be used in the individual concentration-time plots. Nominal times will be used for the purposes of summarization and in mean and median plots. See [Appendix 4: Data Display Standards & Handling Conventions](#). for details on pharmacokinetic figure and table displays.

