### **8.3. Statistical Analyses**

All the derived pharmacokinetic parameters will be summarized and listed for the PP population by study phase and treatment. For each of these PK parameters, with the exception of  $t_{max}$ , the following descriptive summary statistics will be calculated for each treatment: n, arithmetic mean with associated 95% CI, standard deviation, median, minimum, maximum, geometric mean with associated 95% CI, standard deviation of logarithmically transformed data, and the geometric coefficient of variation ( $CV_b(\%)$ ). For  $t_{max}$ , the n, median, minimum, and maximum summary statistics will be provided.

Data display specifications for derived PK parameter summaries and listings are given in [Appendix 9](#) of this RAP

PK samples collected outside the protocol defined time-windows and/or other protocol deviations will be reviewed by the study team to determine whether the sample will be excluded from PK analyses. PK reporting will also consider planned Quality Tolerance Limit (QTL) outcomes affecting study data quality. Details are found in the QTL Report.

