### 11.4.3. Reporting Standards for Pharmacokinetic Data

Pharmacokinetic Concentration Data	
Descriptive Summary Statistics, Graphical Displays and Listings	
Refer to IDSL PK Display Standards. Refer to IDSL Statistical Principle 6.06.1.
 
For continuous data:
 
 
Not quantifiable values (NQs) at the beginning of a participant profile (i.e. before the first incidence of a measurable concentration) are deemed to be zero as it is assumed that in this circumstance no drug is yet measurable in the blood.
 
For NQs at the end of the participant profile (i.e. after the last incidence of a measurable concentration): 
 
for individual plots and pharmacokinetic analyses these are dropped (set to missing) as they do not provide any useful information (and can erroneously indicate that absolutely no drug is present)
 
for summary statistics, these are set to 0 (to avoid skewing of the summary statistics)
 
 
 
Individual NQs which fall between two measurable concentrations are set to missing (individual values of this nature are assumed to be an anomaly).
 
If two or more NQ values occur in succession between measurable concentrations, the profile will be deemed to have terminated at the last measurable concentration prior to these NQs. For the purpose of individual participant plots, these NQs will be set to 0, and the subsequent measurable concentrations will be retained. For the derivation of pharmacokinetic parameters, these NQs and any subsequent measurable concentrations will be omitted (set to missing).
 
 
Note: Concentration values will be imputed as per GUI_51487 for descriptive summary statistics/analysis and summarized graphical displays only.

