### 11.9.6. Pharmacokinetic Tables

Pharmacokinetic: Tables					
No.	Population	GSK Standard / Example Shell	Title	Programming Notes	Deliverable [Priority]
Pharmacokinetic Parameters					
4.1.	PK Parameter	PK_01	Summary of Derived Plasma Cabotegravir PK Parameters by Study Phase		Interim, SAC
4.2.	PK Parameter	PK_01	Summary of Derived Plasma Rilpivirine PK Parameters by Study Phase		Interim, SAC
Pharmacokinetic Concentration					
4.3.	PK Concentration	PK01	Summary of Plasma Cabotegravir PK Concentration (ug/mL)-Time Data by Study Phase and Nominal Timepoint		SAC
4.4.	PK Concentration	PK01	Summary of Plasma Rilpivirine PK Concentration (ng/mL)-Time Data by Study Phase and Nominal Timepoint		SAC

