## Summary of Derived Cabotegravir Pharmacokinetic Parameters by Phase

Parameter	Summary Statistics	Oral CAB 30mg (N=xx)	IM CAB 600 mg (N=xx)
AUC 0-t (h* $\mu$ g/mL)	n	xx	xx
	Mean (SD)	XXX.X (xx.xx)	XXX.X (xx.xx)
	95% CI	(xxxx.xx, xxxx.xx)	(xxxx.xx, xxxx.xx)
	%CV	xx.x	xx.x
	Median	XXX.XX	XXX.XX
	Min, Max	XXX.X, XXX.X	XXX.X, XXX.X
	Geometric mean	XXX.XX	XXX.XX
	95% CI	(xxxx.xxxx, xxxx.xxxx)	(xxxx.xxxx, xxxx.xxxx)
	SD (log)	XXX.XXX	XXX.XXX
	Geometric %CV	XXX.X	XXX.X
AUC 0-<math>\infty</math> (h* $\mu$ g/mL)	n	xx	xx
	Mean (SD)	XXX.X (xx.xx)	XXX.X (xx.xx)
	95% CI	(xxxx.xx, xxxx.xx)	(xxxx.xx, xxxx.xx)
	%CV	xx.x	xx.x
	Median	XXX.XX	XXX.XX
	Min, Max	XXX.X, XXX.X	XXX.X, XXX.X
	Geometric mean	XXX.XX	XXX.XX
	95% CI	(xxxx.xxxx, xxxx.xxxx)	(xxxx.xxxx, xxxx.xxxx)
	SD (log)	XXX.XXX	XXX.XXX

Geometric %CV

xxx.x

xxx.x

/Directory/program.sas 01JAN2002 12:01

---

Programming notes:

- 1) Repeat table for RPV (Oral RPV 25mg, IM RPV 900mg; ng/mL, ng\*h/mL)
- 2) Repeat for all of the following PK parameters as available:  $C_{max}$ ,  $t_{max}$ ,  $t_{1/2}$ ,  $K_A$  LA,  $\lambda_z$ ,  $C_{24}$ ,  $C\tau$
- 3) For  $t_{max}$ , only the n, median, minimum, and maximum should be provided.
- 4) Report the means & median +1 decimal past the maximum length of results within parameter. Report the SD and 95% CI values +2 decimals past the maximum length of results within parameter. %CV statistics should be reported to 1 decimal.

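### The SAP's geometric CV formula leaves the −1 outside the square root; followed as written, it would understate between-participant variability about 3- to 7-fold for Cmax, AUC and CAB KALA

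*SAP*

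**What the plan says.** SAP section 11.5.4 states that all PK parameters except tmax are log-transformed (natural log) for summary statistics. Under the heading for the geometric coefficient of variation it then gives two lines. For untransformed data the formula is 100 × (SD/Mean). For transformed data it is "100 * (\sqrt{\exp(SD_{\log}^2)} - 1", closing the bracket after the 1, with SDlog the standard deviation of the log-transformed data. Neither document gives another formula for this statistic.

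The statistic is widely planned:

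- Protocol section 10.4.1 commits to a between-participant CV for the log-transformed PK parameters.
- SAP section 3.2 says that it, with the geometric mean, "will also be calculated for all parameters except" tmax.
- SAP section 8.3 asks for the "standard deviation of logarithmically transformed data, and the geometric coefficient of variation" for each derived parameter, again leaving out tmax.
- The outputs are Table 4.1, "Summary of Derived Plasma Cabotegravir PK Parameters by Study Phase", and its rilpivirine counterpart, Table 4.2. Both are marked for the interim and the final deliverable.
- The mock display PK_01 has separate rows for %CV, SD (log) and Geometric %CV, and its programming notes say that "CV statistics should be reported to 1 decimal".

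SAP section 8.1 also lists "percentiles and the geometric coefficient of variation" for the concentration summaries. For concentration data, however, section 11.4.3 says "Refer to IDSL PK Display Standards", and that standard is not reproduced in the SAP.

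**The concern.** If X is log-normal and SDlog is the standard deviation of ln X, then SD(X)/mean(X) = sqrt(exp(SDlog²) − 1). The −1 belongs under the root. With the −1 outside, the square root merely halves the exponent, and the result, exp(SDlog²/2) − 1, is not a coefficient of variation. It is how far the mean of X exceeds its median, as a fraction of the median.

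The study tests no hypothesis, and its primary objective is to describe the PK profiles after thigh injection. Between-participant variability is part of that description, and the geometric CV is a planned summary of it. A program that followed section 11.5.4 literally would give a wrong Geometric %CV for every primary PK parameter except tmax. PK_01 would also print it a few rows below an arithmetic %CV that is several times larger.

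**Working it through.** The documents state no CV value, so there is no planned figure to reproduce. The check compares the written formula with the log-normal CV, first algebraically and then at spreads the protocol itself supplies.

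**Algebra.** Let a = exp(SDlog²/2). The correct CV is sqrt(a² − 1) and the written form is a − 1. Their ratio is sqrt(a² − 1)/(a − 1) = sqrt((a + 1)/(a − 1)), which exceeds 1 whenever SDlog > 0. The written value is therefore always too low. For small SDlog the ratio is close to 2/SDlog, so the relative error is worst where variability is least.

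**Inputs.** Protocol Table 2 gives medians with 90% prediction intervals for a single gluteal injection; CAB Cmax, for example, is "2.13 (0.69, 5.80"). Under log-normality SDlog = ln(upper/lower)/(2 × 1.645) = ln(upper/lower)/3.29.

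**Worked case, CAB Cmax.**

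- SDlog = ln(5.80/0.69)/3.29 = 0.647, so exp(SDlog²) = 1.520.
- Correct: 100 × sqrt(1.520 − 1) = 72.1%.
- As written: 100 × (sqrt(1.520) − 1) = 23.3%.

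**All cases used.** Table 2 does not give AUC(0-t) or AUC(0-∞), so AUC(0-Week 52) stands in for both.

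| Parameter | 90% interval | SDlog | Correct CV% | As written % | Ratio | Ratio, half-intervals |
|---|---|---|---|---|---|---|
| CAB Cmax | 0.69 to 5.80 | 0.647 | 72.1 | 23.3 | 3.1 | 2.9–3.3 |
| RPV Cmax | 21.2 to 151 | 0.597 | 65.4 | 19.5 | 3.4 | 3.3–3.4 |
| CAB KALA | 0.0002 to 0.0018 | 0.668 | 75.0 | 25.0 | 3.0 | 2.8–3.2 |
| CAB AUC(0-Wk52) | 2240 to 5868 | 0.293 | 29.9 | 4.4 | 6.8 | 6.7–7.0 |
| RPV AUC(0-Wk52) | 58332 to 182124 | 0.346 | 35.7 | 6.2 | 5.8 | 5.7–5.9 |

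The last column takes SDlog from one side of the interval only, ln(median/lower)/1.645 or ln(upper/median)/1.645. The result does not depend on the intervals being symmetric on the log scale. The shorter AUC intervals in Table 2 give ratios between these extremes (for example 3.4 for CAB and 3.6 for RPV at Week 4).

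RPV KALA and RPV half-life are left out. The two halves of the RPV KALA interval imply SDlog of 0.004 and 0.071, so no single value can be taken from it. CAB half-life carries the same information as CAB KALA.

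**Simulation checks.**

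- With 3 million log-normal draws, SD/mean was 0.2993 at SDlog 0.293 and 0.7210 at SDlog 0.647. The correct formula gives 0.2994 and 0.7210; the written one gives 0.0439 and 0.2328.
- At the planned size of 15 participants (200,000 simulated studies per case), the medians of arithmetic %CV, correct geometric CV and written form were 63.0, 70.0 and 22.0 for CAB Cmax; 28.6, 29.2 and 4.2 for CAB AUC; and 33.8, 34.8 and 5.9 for RPV AUC. The 5th to 95th percentiles of the correct-to-written ratio were 2.4–4.5, 5.2–10.0 and 4.5–8.4 respectively.

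**The case against.** The strongest objection is that the point turns on where one radical bar ends, in text that a program read from a PDF. If the bar covers the −1 in the source, there is no error. The outer brackets do not settle it, because the line for untransformed data also has brackets it does not need. Probable misreadings occur elsewhere, such as the garbled name of Hy's Law in a footnote to protocol Appendix 6. On the other side, the QTc formulas in SAP section 11.5.3 contain several radicals, some with compound terms under the root, and all read correctly. A misreading is therefore possible but not shown, and the source has to be checked.

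A second objection is that the program may not follow this line. SAP section 11.4.2 applies the sponsor's display standards unless otherwise stated, and neither those standards nor any code is available. That stands: the finding concerns the written definition, not a reported result.

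Third, the impact is small. SD (log) is in the row directly above Geometric %CV in PK_01, so a reader can recompute the statistic, and a 4% geometric CV beside an arithmetic CV near 29% should be noticed at quality control. This limits the seriousness but does not make the formula right.

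Finally, the sizes are illustrative. AUC(0-Week 52) is an imperfect stand-in for RPV AUC(0-∞): with Table 2 medians, and taking KALA as the terminal slope, the part beyond Week 52 is about 3.24/0.000146 ≈ 22,200, or 22,200/(102,380 + 22,200) ≈ 18% of the total. The direction of the error does not depend on this.

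**Conclusion.** The concern holds on the SAP text available. The only geometric CV formula in either document is not the log-normal CV and is too low at every positive SDlog. At the protocol's own predicted spreads the shortfall is about 3-fold for Cmax and CAB KALA and about 6- to 7-fold for AUC to Week 52. Those sizes rest on log-normality, on thigh spread resembling the gluteal predictions, and on AUC(0-Week 52) as a stand-in.

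Confidence is moderate, because the extent of the radical must be confirmed in the source. The damage is confined to one descriptive statistic: no estimate, confidence interval, population rule or decision uses it. The concentration summaries are affected only if the same formula is applied there. It should be corrected, but it does not threaten the study's conclusions.

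**What to change.** 1. Check the source PDF of SAP section 11.5.4. If the bar covers the −1, no change to the formula is needed.
2. If it does not, replace the line for transformed data with: CVb% = 100 × sqrt(exp(SDlog²) − 1).
3. Confirm that the program for Tables 4.1 and 4.2 uses this form, for the interim as well as the final delivery.
4. State whether the same formula applies to the concentration summaries in Tables 4.3 and 4.4.
5. Optionally, label 100 × (SD/Mean) as the arithmetic %CV. It now sits under the geometric heading, while PK_01 already has separate rows.

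The cost is one source check, one line of SAP text and one program check. Design, data collection and all other statistics stay as they are.

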#### 11.5.5. Health Outcomes

**CONFIDENTIAL**

208832

CCI

## 11.6. Appendix 6: Reporting Standards for Missing Data

### 11.6.1. Premature Withdrawals

Element	Reporting Detail
General	
 
Withdrawn participants may be replaced in the study. All subjects who withdraw prematurely from the study/study drug will be documented and the reason for their withdrawal recorded in the final Clinical Pharmacology Study Report (CPSR).
 
All available data from participants who were withdrawn from the study will be listed and all available planned data will be included in summary tables and figures, unless otherwise specified.
 
Withdrawal visits will be slotted according to Appendix 2: Assessment Windows
 

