4. Two consecutive approved molecular tests (PCR or antigen test) must be conducted on all study participants and separated by >48 hours. Following the second test for SARS-CoV-2, participants should be quarantined within the unit. Once the second test is negative, the participant can be released into the unit and follow Infection Control practices
5. Oral CAB and RPV dosing Days 1 to 28. Day 1, Day 2, and Day 14 doses should be administered in the clinic.
6. PK sampling – On Day 1 - 1h, 2h, 3h, 4h, 6h, 8h, and 12h, and Day 2 PK between 22 to 26 h post first oral dose. On Day 14 pre-dose samples. Day 29 PK should occur between 22 to 26 hours from the last dose on Day 28. Total of 20 PK samples (10 for CAB, 10 for RPV assay) will be collected during oral lead-in phase. Please refer to Section 8.4 for permitted PK window for OLI phase.
7. AE assessment will include a brief, symptom-directed physical exam as needed.
8. Genetic sample - collect the sample at the earliest convenient time after the first dose in the oral lead in phase on Day 1.
9. If a participant is withdrawn prior to receiving the CAB LA and/or RPV LA injection, a follow-up/withdrawal visit should be scheduled 10-14 days after the last oral dose of CAB and RPV.

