## **7.2. Participant Discontinuation/Withdrawal from the Study**

- A participant may withdraw from the study at any time at his/her own request or may be withdrawn at any time at the discretion of the investigator for safety, behavioral, compliance or administrative reasons. This is expected to be uncommon.
- At the time of discontinuing from the study, if possible, an early withdrawal visit should be conducted. See SoA for data to be collected at the time of study discontinuation and follow-up and for any further evaluations that need to be completed.
- The participant will be permanently discontinued both from the study intervention and from the study at that time.
- If the participant withdraws consent for disclosure of future information, the sponsor may retain and continue to use any data collected before such a withdrawal of consent.
- If a participant withdraws from the study, he/she may request destruction of any samples taken and not tested, and the investigator must document this in the site study records.

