## 11.2. Appendix 2: Assessment Windows

All assessments/events (including those from planned, unscheduled and withdrawal visits) will be assigned to assessment windows/analysis visits according to actual dates of collection rather than the nominal visit labels recorded on the eCRF or in the laboratory database. All assessment data, including unscheduled data will be presented in listings.

For parameters which are not scheduled to be assessed at a particular visit, the all-inclusive assessment windows will still be used; however, data displays summarizing measurements by visit will only report visits in which the parameter is a planned collection according to [Appendix 1: Schedule of Activities](#)

Note: Prior to visit slotting, assessments are first assigned to a study phase according to [Table 3](#).

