### 11.2.1. Definitions of Assessment Windows

**Table 8 Assessment Windows for Screening and OLI Phase Data**

Parameter	Analysis Window	Target Period Day	Analysis Timepoint
Assessments assigned to Phase=Screening or OLI (per Table 3)			
All	OLI Phase Day <1	The day of earliest record	Screening
PK, Vital Signs, Labs, ECG	OLI Phase Day = 1	1	Day 1
PK, Vital Signs, Labs	OLI Period Day = 2	2	Day 2
PK	13 ≤ OLI Phase Day ≤ 15	14	Day 14
Vital Signs, Labs	3 ≤ OLI Phase Day ≤ 21	14	Day 14
PK	28 ≤ OLI Phase Day ≤ 30	29	Day 29
Vital Signs, Labs, ECG	22 ≤ OLI Phase Day	29	Day 29
If none of the above			Day X, where X=OLI Phase day

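### Labs and vital signs from the oral-phase withdrawal visit, taken 10-14 days off drug, are slotted by date into the Day 14 or Day 29 summaries; PK samples are at risk only on a few days

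*SAP*

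**What the plan says.** **When the visit takes place.** Protocol 1.3.1, footnote 9, states that for a participant withdrawn before injection "a follow-up/withdrawal visit should be scheduled 10-14 days after the last oral dose of CAB and RPV". Protocol 4.1.4 and the SAP's copy of the schedule (11.1.1) agree. The SAP schedule marks vital signs, haematology and chemistry, and PK in the Early Withdrawal column, but not ECG. Protocol 7.2 gives a different time: "At the time of discontinuing from the study, if possible, an early withdrawal visit should be conducted".

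**How it is slotted.** SAP 11.6.1 states "Withdrawal visits will be slotted according to Appendix 2: Assessment Windows". SAP 11.2 says that assessments, expressly including withdrawal visits, "will be assigned to assessment windows/analysis visits according to actual dates of collection rather than the nominal visit labels". SAP 11.6.1 also says that for withdrawn participants "all available planned data will be included in summary tables and figures, unless otherwise specified".

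**The windows.** In SAP Table 8 the labs and vital-signs window for Day 14 is "3 ≤ OLI Phase Day ≤ 21". The window for Day 29 is Day 22 onward, with no upper limit. The PK window for Day 14 is "13 ≤ OLI Phase Day ≤ 15", and for Day 29 it is Days 28-30. Any other PK sample is labelled Day X. There is no withdrawal timepoint and no condition on the last dose. SAP 11.3.1 leaves the OLI phase without an end date for participants who are never injected. SAP 11.5.1 uses the value nearest the target day when several share a window, and the mean if they are equally near.

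**The concern.** Completers reach Day 14 on drug and Day 29 within a day of their last dose. A participant who stopped early reaches the withdrawal visit after what Protocol 4.2.1 treats as an adequate washout. Table 8 does not separate the two, so values on drug and off drug are averaged in the same row under the column that names oral CAB plus oral RPV.

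The participants concerned may have stopped because of a safety finding. Someone whose last dose was on Day 14, stopped for a raised ALT, returns on Days 24-28, and that possibly recovered ALT is summarised as Day 29. Someone whose last dose was on Day 5 returns on Days 15-19 and becomes a Day 14 value. For PK, a washed-out sample could enter the Day 14 or Day 29 trough summaries, and Day 29 also supplies the OLI Cτ parameter in SAP Table 7.

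**Working it through.** The plan gives no figure of its own on this point. The check applies its rules to every possible case.

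**Set-up.** The first oral dose is Day 1. Let L be the day of the last oral dose (1-28) and g the gap to the visit (10-14 days). The visit falls on OLI Day L + g. This gives 28 × 5 = 140 combinations, counted with equal weight; they are not a forecast of participants.

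**Labs and vital signs (Table 8)**

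| L | Visit day | Slot | Combinations |
|---|---|---|---|
| 1-7 | 11-21 | Day 14 | 35 |
| 8-11 | 18-25 | Day 14 or Day 29 | 10 + 10 |
| 12-27 | 22-41 | Day 29 | 80 |
| 28 | 38-42 | Day 29 window, but the real Day 29 visit is closer | 5 |

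All 140 fall in a window: 45 in Day 14 and 95 in Day 29. If no other assessment lies in the same window, the off-drug value is the one summarised in 45 + 90 = 135 combinations, which covers every L from 1 to 27.

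**If there is also a visit at discontinuation (Protocol 7.2).** Assume it takes place on Day L + 1 and apply the closest-to-target rule to the 135:
- in 60 combinations the discontinuation visit lies in another window, so the withdrawal value is still alone (Day 14: L = 1, 5 combinations; Day 29: L = 8-11, 10, and L = 12-20, 45);
- in 38 the withdrawal value is the closer one (29 in Day 14, 9 in Day 29);
- in 4 the two tie and are averaged;
- in 33 the discontinuation visit wins.

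So 60 + 38 + 4 = 102 of 135 still put an off-drug value into the summary. For example, with L = 10 the Day 11 visit is 3 days from target and beats a withdrawal visit on Day 20 or 21 (6 or 7 days away). A withdrawal visit on Days 22-24 goes to Day 29 unopposed.

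**Weight of one value.** Protocol 10.2 plans about 15 injected participants. One value carries 1/15 = 6.7% of a mean over 15, or 1/16 = 6.25% over 16. The documents do not allow an estimate of the resulting shift in any laboratory or vital-sign mean.

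**PK windows.**
- Days 13-15 are reached by L = 1-5: 3 + 3 + 3 + 2 + 1 = 12.
- Days 28-30 are reached by L = 14-20: 1 + 2 + 3 + 3 + 3 + 2 + 1 = 15.
- Together 27 of 140 (19%). The other 113 (81%) become Day X, which is not a planned visit and is not summarised.

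**Size if a PK sample is mis-slotted and kept.** At 7-10 half-lives the residual is 2^-7 = 0.78% to 2^-10 = 0.10%. With one such value among n and the others equal:
- geometric mean falls by 1 - 2^(-7/n) to 1 - 2^(-10/n): 26-35% for n = 16, 28-37% for n = 15;
- arithmetic mean falls by 1 - (n - 1 + 2^-7)/n: 6.2% for n = 16, 6.6% for n = 15.

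These figures need a quantifiable result. SAP 11.4.3 sets a non-quantifiable value at the end of a profile to zero in summary statistics, and the geometric-mean formula does not apply to a zero.

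**Likely reach.** Protocol 2.2 reports (283 - 278) + (308 - 303) = 10 of 591 participants (1.7%) who had the oral lead-in but no injection in two Phase 3 studies. At that rate 16 participants would yield 16 × 10/591 = 0.27 cases. Those were HIV-infected patients, so this is only illustrative.

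**The case against.** **PK.** A reader might infer that withdrawal PK samples are generally reported as troughs. The documents do not support that. Four in five combinations miss both PK windows. SAP 8.1 says nominal times are used for PK summaries, and Tables 4.3 and 4.4 are organised by nominal timepoint; a withdrawal sample has no Day 14 or Day 29 nominal time. SAP 8.3 sends samples outside the protocol windows, or affected by other deviations, to study-team review, and Protocol 8.4 defines Day 29 as 22-26 hours after the Day 28 dose. This objection largely stands. What remains is that SAP 11.2 (actual dates) and SAP 8.1 (nominal times) conflict, and that the review has no stated rule. The protocol's Day 14 window is plus or minus one day, so a sample on Days 13-15 would not stand out by date alone.

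**Safety signal.** A reader might also infer that a liver or vital-sign effect would be hidden. It would not. Under SAP 11.5.1 all valid assessments count toward maximum grade (Tables 3.27 and 3.30). Liver events and hepatobiliary abnormalities have Tables 3.32 and 3.33 and Listings 32 and 33. Adverse events leading to discontinuation have Table 3.12, and laboratory data are listed. In the ALT example the raised Day 14 value stays at Day 14, and under the fix that person simply has no Day 29 value.

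**Washout belongs to the oral phase.** SAP 5.1 counts washout safety events with the oral lead-in, so Day 14 and Day 29 could be read as time labels only. But that sentence concerns events. It does not justify averaging a washed-out value with values taken within a day of dosing.

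**Small reach.** Few oral-phase withdrawals are likely, and the tables are descriptive. This bears on priority; the rule still mislabels any case that occurs.

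**Conclusion.** The point holds for labs and vital signs. As written, any participant whose last oral dose is on Day 1-27 and who attends the 10-14 day visit supplies an off-drug value to the Day 14 or Day 29 by-visit summaries, unless another value is closer to target. The consequence is dilution or mislabelling of descriptive change-from-baseline tables, with a weight of 6-7% per value at the planned size.

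For PK it is a conditional risk. The last dose must fall on Day 1-5 or Day 14-20, the sample must fall on Days 13-15 or 28-30, actual-date slotting must prevail over nominal time, and the sample must survive review.

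The injection-phase primary PK endpoints are untouched. The conclusion rests on the protocol's half-life statement being taken for both drugs, and on the withdrawal visit being held when footnote 9 says. The competing timing in Protocol 7.2 means that one label could hold values on drug or off drug.

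**What to change.** - In SAP 11.6.1 and Table 8, give the oral-phase withdrawal visit its own analysis timepoint, keyed to the last oral dose date. Exclude it from the Day 14 and Day 29 by-visit summaries and from the PK trough summaries, and keep it in the listings and worst-grade tables. The sponsor should set the cut-off after the last dose.
- State in SAP 11.2 that PK concentration summaries use nominal timepoints, so that it agrees with SAP 8.1 and Tables 4.3 and 4.4.
- Reconcile the timing of the withdrawal visit between Protocol 7.2 and Protocol 4.1.4 with footnote 9 of the schedule.

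The cost is SAP wording and one slotting condition. The oral stop date is already used for exposure in SAP 11.5.3, so no new data are needed. The downside is that by-visit n is smaller by the number of oral-phase withdrawals. SAP 11.9 still describes the display list as tentative, so the change is cheap to make.
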